There are no special precautions needed in this study. Standard disinfection policies apply. Personal protective equipment and standard protocol should be followed at all times. Patient safety and privacy will be addressed at all times.

Confidentiality

Persons who are primary investigators and secondary investigators, along with the IRB, will have access to patient records. To protect patient privacy and confidentiality, each patient will be assigned a subject identification number. Names will not be included in the data analysis. The investigators will strictly adhere to HIPAA and IRB guidelines to ensure that patient confidentiality is maintained.

Plans for Data Analysis

Data for each subject will be recorded in RedCap which will only be accessed by study investigators. Means and standard deviation will be calculated for age, gender, race, heart rate,

and pulse oximeter reading from hospital-grade and smartphone pulse oximeters. A t-test will be used to determine any significant association between age, gender, diagnosis, weight, and oxygen use ($p < .05$). Alpha will be used as 0.05 and beta will be used as 0.20. It can be predicted that these tests will be parametric. A scatter plot will be used to assess bias and validity.

Independent variables: Type of pulse oximeter

Dependent variables: SpO₂ and heart rate

Co-variables: body mass index, admitting diagnosis, age, site of measurement, oxygenation status, skin pigmentation, nail color, and pulmonary disorders.

References

1. Topol E. How technology is transforming healthcare. 2013;2017(08/02). Web.
2. Huston C. The impact of emerging technology on nursing care: warp speed ahead. *Online J Issues Nurs* 2013;18(2):1.
3. Ventola CL. Mobile Devices and Apps for Health Care Professionals: Uses and Benefits. *P T* 2014;39(5):356-364.
4. Heath S. mHealth App Market Sees \$400 Million Growth in Five Years. 2015;2017(08/03). Web.

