Appendix

Subject ID _____

Gender Male Female Transgendered

Ethnicity White/Caucasian
 Hispanic/Latino
 Black/African American
 Asian
 Other (specify) _____

Age _____

Weight (lbs) _____

Diagnosis Asthma
 Congestive obstructive pulmonary disorder (COPD)
 Cystic Fibrosis
 Pulmonary Fibrosis
 Chronic Bronchitis
 Bronchiectasis
 Congestive Heart Failure
 Stroke
 Heart Attack/Failure
 Pulmonary Hypertension
 Cancer
 Renal Disease
 Other (specify) _____

Oxygen use? Yes No

If yes, indicate the amount of oxygen used

○ ○ ○ ○ ○
< 2L/min flow 2-6 L/min flow 6-10 L/min flow As needed Only after physical activity

	Pre-test Vital Signs			Post-test Vital Signs		
	Masimo	Kenek/Apple	Samsung	Masimo	Kenek/Apple	Samsung
Heart Rate						
SpO ₂						
Blood Pressure						
RR						
Borg Dyspnea Scale

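### The one significance test named, a t-test, has no stated outcome and fits only yes/no oxygen use as collected; age, weight, gender and diagnosis need another model or unstated splits

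*Combined protocol and SAP*

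**What the plan says.** Plans for Data Analysis contains one sentence that names a test: "A t-test will be used to determine any significant association between age, gender, diagnosis, weight, and oxygen use", judged at p < .05. It is followed by "Alpha will be used as 0.05 and beta will be used as 0.20" and "It can be predicted that these tests will be parametric". The rest of the section is means and standard deviations, plus a graph: "A scatter plot will be used to assess bias and validity".

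The same section then gives the roles of the variables: "Independent variables: Type of pulse oximeter" and "Dependent variables: SpO₂ and heart rate". Age and diagnosis appear in the list of co-variables. The t-test sentence itself mentions neither the device nor either reading.

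The data collection form in the Appendix shows how the five items are recorded. Age and weight are open fields. Gender has three options ("Gender Male Female Transgendered"). Diagnosis is a list beginning "Diagnosis Asthma" that runs to 12 named conditions plus an Other box. Oxygen use is yes or no, with a further item on amount if yes. No cut-point for age or weight and no grouping of diagnoses is given anywhere, and no regression, correlation, analysis of variance or categorical test is named.

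**The concern.** A two-sample t-test compares the mean of a numeric variable between two groups. Most of the items listed in the sentence do not supply two groups, and the sentence does not say what numeric variable is to be compared.

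An analyst who follows the text therefore has to make up the analysis after the data are in: where to cut age and weight, which diagnoses to put together, what to do with the third gender option, or which other method to use. Choices made with the results in view weaken any p-value that follows, and cutting a continuous variable also throws information away. A test taken one factor at a time cannot separate, for example, oxygen use from the diagnosis that led to it. At stake is whether the study can say anything dependable about which patients get less accurate phone readings.

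**Working it through.** This is a question of fit between method and data, so there is no figure in the plan to reproduce. The inputs are the t-test sentence and variable roles (Plans for Data Analysis), the recording of each item (Appendix form), and the two stated sample sizes, 48 (Experimental Design and Methods) and 30 (Inclusion criteria). The check holds at either size.

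**Reading 1: each item against the device readings.** This takes SpO₂ and heart rate as the outcomes, as the list of dependent variables does.

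| Item | As collected | Two groups? |
|---|---|---|
| Age | number | no |
| Weight | number (lbs) | no |
| Gender | 3 options | no, unless reduced to 2 |
| Diagnosis | 13 options | no |
| Oxygen use | yes/no | yes |

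One of five items fits as collected, and two of five if gender is reduced.

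**Reading 2: associations among the five items, as the words literally run.** There are 5 × 4 / 2 = 10 pairs.

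- Number by two groups: age or weight by oxygen use (2 pairs), and age or weight by gender if reduced to two levels (2 pairs). A t-test fits these 4.
- Number by number: age by weight (1 pair). Does not fit.
- Number by 13 options: age or weight by diagnosis (2 pairs). Does not fit as listed.
- Category by category: gender by diagnosis, gender by oxygen use, diagnosis by oxygen use (3 pairs). Does not fit.

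The total is 4 + 1 + 2 + 3 = 10. A t-test fits 4 of 10 at most, and 2 of 10 with gender as collected.

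**Illustration only: what a median split would cost.** The plan does not propose one; this prices one way an analyst might make age or weight fit a t-test. For a normally distributed predictor, the squared correlation between the variable and its median split is 2/π = 0.637. In large samples the split analysis is worth that fraction of the patients: 48 × 0.637 = 30.6, about 31; 30 × 0.637 = 19.1, about 19.

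A simulation (40,000 runs; bivariate normal data; two-sided 0.05, since the plan does not state sidedness) agrees. The correlation was chosen so that the continuous analysis has about 81% power:

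| n | Assumed correlation | Power, kept continuous | Power, median split |
|---|---|---|---|
| 48 | 0.39 | 81% | 60% |
| 30 | 0.49 | 81% | 59% |

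**How much a replacement model can carry.** Age, weight and oxygen use take one coefficient each. Gender takes one or two (two or three levels), and diagnosis one or two (two or three groups). That is 5 to 7 coefficients besides the intercept. Patients per coefficient run from 48/7 = 6.9 to 48/5 = 9.6 at n = 48, and from 30/7 = 4.3 to 30/5 = 6.0 at n = 30. This is thin, so the results can only be exploratory.

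**The case against.** Four things can be said for the plan.

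First, on the literal reading some t-tests are perfectly valid: age and weight can each be compared between oxygen users and non-users. This stands. A reader might infer that a t-test is useless for nearly everything listed; the documents do not support that, because the sentence never says that the device readings are the outcome. What remains is that most pairs still do not fit, and that the reader cannot tell which comparison is meant.

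Second, a regression slope or a correlation is itself tested with a t statistic, and needs no split. So a reader who calls the analysis invalid, or says it forces arbitrary cut-points, goes too far. But the plan names neither method, so the sentence cannot be carried out as written for those items.

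Third, the diagnosis list need not be 13 exclusive groups. The form has no instruction to choose one, and some boxes overlap (COPD with chronic bronchitis, for example). Each diagnosis could be coded present or absent, and a two-group test would then fit. This also stands. It is why no estimate is given here of the cost of comparing every diagnosis with every other, a scheme that the plan does not propose. The plan does not propose present/absent coding either.

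Fourth, these are analyses of patient characteristics. The aim is accuracy against the Masimo, and the plan assigns bias and validity to a scatter plot. This is right, and it settles the weight of the point.

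**Conclusion.** The point holds in a limited form, as something that should be fixed. The only named test has no stated outcome. Against the device readings it fits one of the five items as collected (two if gender is reduced to two levels); among the items themselves it fits at most 4 of 10 pairs. The other comparisons need splits, groupings or another model that the plan does not state.

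A reader might infer that the study's main result rests on an invalid test. The documents do not support that: the sentence mentions no device, and an error in it would leave the phone-versus-Masimo comparison unchanged. Whether a scatter plot is enough for that comparison, and which of 48 or 30 is the intended sample size, are separate questions.

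The counts rest on the form as printed. The information loss of about 36% (1 − 0.637) applies only if a median split were used on a roughly normal predictor, and it is not a loss built into the plan.

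**What to change.** Replace the t-test sentence with a specification along these lines:

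- **Response:** the phone-minus-Masimo difference at the same time point, with one linear model for each phone (Kenek/iPhone, Samsung) and each outcome (SpO₂, heart rate). That is 2 × 2 = 4 models.
- **Pre- and post-test readings:** either fit the two separately (8 fits), or fit them jointly with a pre/post term and a patient random effect. State which. Pooling both readings as if they came from different patients would be wrong.
- **Covariates:** age and weight continuous; oxygen use yes/no; gender categorical, with a stated rule for sparse levels; diagnosis in two or three groups fixed before analysis. Add a rule for patients with more than one diagnosis, for example present/absent indicators for broad groups.
- **Reporting:** slopes or adjusted mean differences with 95% confidence intervals, labelled exploratory because n is 48 or 30.

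If associations among the patient characteristics are wanted as well, say so and name a method for each type of pair: correlation for age with weight, Fisher's exact test for categorical pairs, and a t-test only where there are two groups.

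The cost is a rewritten paragraph and a little more analysis work. Every field needed is already on the form, and the SPSS software already planned can fit these models. The drawback is few patients per coefficient (about 4 to 10, as shown above), so intervals will be wide, and the diagnosis groups should be kept few.

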Study Title:

The Accuracy of Smartphone Pulse Oximetry in Patients Visiting an Outpatient Pulmonary Function Lab for a 6-Minute Walk Test

Primary Investigator:

[name], RRT-ACCS, AE-C, FAARC, FCCP
Director of Clinical Education
Assistant Professor
Rush University, Department of Respiratory Care

Co-Investigator:

[name]
M.S. in Respiratory Care | Class of 2018
Department of Respiratory Care
Rush University Medical Center

[name], MS, RRT, RPFT
Pulmonary Function Lab
Rush University Medical Center

October 13, 2019

Aim of the Study

The primary aim of this research is to determine the accuracy of smartphone pulse oximeters in detecting blood oxygen saturations, episodes of desaturations, and heart rate by comparing results to a Masimo[©] hospital-grade pulse oximeter.

Introduction

Digital innovations have made it possible for consumers to use mobile devices for medical purposes. They can be used to monitor physiological parameters such as blood pressure, heart rate, blood oxygen saturation, and body temperature. They can also be used to conduct diagnostic tests, request prescription refills, and relay medical information to physicians.¹ Consequently, the healthcare sector is being profoundly affected by this emerging technology.^{1,2} A frequent reliance on mobile devices has been reported among healthcare practitioners (HCPs) and students, with 85% reporting the use of a mobile device at least once daily for clinical purposes. The most common use was for information, time management, or communication relating to education and patient care.³ In 2010, approximately 50 percent of physicians used a mobile phone or a smart mobile device as a part of his or her practice. In 2015, that number increased to approximately 70 percent. The overall growth of applications (apps) was 38.1 percent, compounded annually over the past five years; in regards to medical apps, the growth was documented at 41.9 percent.⁴

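### The plan's only hypothesis test is an open search for associations at p < .05, with no defined family of tests, no multiplicity control and no exploratory label

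*Combined protocol and SAP*

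**What the plan says.** All of this is in the combined protocol and SAP.

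- **Plans for Data Analysis, test.** A t-test is to look for "any significant association between age, gender, diagnosis, weight, and oxygen use ($p < .05". The sentence does not say whether the t-test is paired or independent, or one- or two-sided. Apart from this test, the section offers only means, standard deviations and a scatter plot.
- **Plans for Data Analysis, error rates.** "Alpha will be used as 0.05 and beta will be used as 0.20". Neither figure is tied to an endpoint or to a set of tests.
- **Plans for Data Analysis, variable list.** "Independent variables: Type of pulse oximeter" and "Dependent variables: SpO₂ and heart rate". Eight co-variables follow, partly overlapping the five factors, with no account of how they will be analysed.
- **Aim of the Study.** The primary aim is to "determine the accuracy of smartphone pulse oximeters in detecting blood oxygen saturations, episodes of desaturations, and heart rate", so it covers several quantities and ranks none first.
- **Procedures and Appendix.** Two phone devices and the Masimo reference are read before and after the walk. The data form repeats the device columns for the two times: "Masimo Kenek/Apple Samsung Masimo Kenek/Apple Samsung".

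No section adjusts for multiple tests, orders them, or calls them exploratory.

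**The concern.** A rule that accepts any p below .05 from a set of tests does not hold the error rate at 5% for the set. It holds it for each test alone, and the overall rate grows with the number of tests. Here that number cannot be read from the plan, so someone who sees one p below .05 in the report cannot tell how many chances there were to obtain it.

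What is at stake depends on what is tested. If the factors are tested against device readings or errors, which is the use that would serve the aim, a chance result could be reported as phone accuracy differing by diagnosis, age or oxygen use. The Introduction says that evidence in patients with lung disease is lacking and that missed desaturations could be harmful. Such a claim would then have little other evidence to check it against.

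**Working it through.** **The plan's own figures.** The plan gives no number of tests and no overall error rate, so there is none to reproduce. The sample size (48 under Experimental Design and Methods, 30 under Inclusion criteria) cannot be reproduced either, because no effect size or standard deviation is given. Neither gap affects the calculation below.

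**Inputs.** Per-test level 0.05; five factors; two dependent variables (Plans for Data Analysis); two phones and two reading times (Procedures). Two-sided tests and all nulls true are assumptions.

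**Formula.** For k independent tests, P(at least one false positive) = 1 − 0.95^k, and the expected number of false positives is 0.05k.

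| Reading of the sentence | k | Chance of at least one | Expected number |
|---|---|---|---|
| Five factors, one outcome | 5 | 1 − 0.774 = 22.6% | 0.25 |
| All pairs among the five factors, 5 × 4 / 2 | 10 | 1 − 0.599 = 40.1% | 0.5 |
| 5 × 2 outcomes × 2 phones (or × 2 times) | 20 | 1 − 0.358 = 64.2% | 1.0 |
| 5 × 2 phones × 2 outcomes × 2 times | 40 | 1 − 0.129 = 87.1% | 2.0 |

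The chance first passes one half at k = 14 (51.2%; k = 13 gives 48.7%).

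**Correlation.** Readings on the same patient are not independent. The documents give no correlations, so a range was simulated: all nulls true, five factors split at the median, outcomes equally correlated at rho, n = 30 and n = 48, factors independent or moderately correlated, 6,000 runs per setting. The ranges cover both sample sizes and both factor settings.

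- 40 tests: about 82-84% at rho 0.3, 76-77% at 0.5, 56-58% at 0.8, 39-40% at 0.95.
- 20 tests: about 55-58% at rho 0.5 and 44-46% at 0.8.

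The expected number of false positives stays near 0.05k throughout. The results barely differ between n = 30 and n = 48, so the conflict in sample size does not matter for this point.

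**What could raise the count.** The form lists 13 diagnosis options. If each were compared yes against no (an assumption), one outcome on one phone at one time would need 13 + 4 = 17 tests, and 1 − 0.95^17 = 58% if independent. Sparse diagnoses might drop out. Testing the further co-variables would add more.

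**The case against.** A reader might infer that the plan tests every factor in every phone, outcome and time combination, and that a false association is therefore likely. The documents do not support that as a statement of fact. The t-test sentence names five factors and nothing else. The 40-test grid comes from joining it to the variable list, the reading schedule and the form, and the form shows what is recorded, not what is tested. On the narrower readings the chance is 23% or 40%, and very strong correlation brings even the 40-test figure down to 39-40%. This objection stands: neither the grid nor the word likely can be asserted without condition.

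On the literal reading, with factors tested against each other, the result says nothing about phone accuracy, so the harm described above would not arise. Some of those pairs, such as weight with gender, may also be truly related, so 40% is not a realistic false-finding rate for them. This stands too. That reading, however, serves no part of the stated aim.

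It can also be said that adjusting factor analyses in a small observational convenience sample is partly convention, and that the tests cannot be counted until the outcome, the type of t-test and the grouping of age, weight and diagnosis are defined. Both are fair. They argue against a formal correction, and for labelling the analyses as exploratory. They do not justify keeping an unqualified rule of p < .05.

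**Conclusion.** The concern holds as a defect of definition. The plan's only hypothesis test is an open search at p < .05 with no stated family of tests, no primary outcome or time point, no multiplicity control and no exploratory label. With all nulls true and independent tests, the chance of at least one false association is about 23% to 87%, depending on how the sentence is read. The narrowest of these readings is already more than four times the nominal 5%. Correlation brings the top of the range down to about 56-58% at rho 0.8.

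The figures rest on all nulls being true, two-sided tests and assumed correlations. The documents do not settle which count applies, so no single figure in the range can be attributed to the plan.

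**What to change.** Replace the significance rule in Plans for Data Analysis with a statement such as: the relation of age, gender, diagnosis, weight and oxygen use to the phone-minus-Masimo differences in SpO₂ and heart rate is exploratory; every such analysis carried out will be reported, for each phone and time point, as an estimate with a 95% confidence interval; no claim of statistical significance will be made from these analyses.

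**Cost.** The wording change is short, but it must also define the phone-minus-Masimo difference, which the plan does not yet do. No data collection changes. The downside is that the study can no longer declare a patient factor significant.

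**An alternative that is harder to recommend.** Holm's correction could be applied on one outcome over five factors and two phones, with a first step of 0.05 / 10 = 0.005. This treats the 13-option diagnosis as a single test and leaves out heart rate, which is part of the aim. It also costs power. With two equal groups, 80% power and a normal approximation, the detectable difference is (z for 1 − α/2 + 0.842) × √(2 / (n/2)). At n = 48, moving from α = 0.05 to 0.005 raises it from (1.960 + 0.842) × 0.289 = 0.81 SD to (2.807 + 0.842) × 0.289 = 1.05 SD. At n = 30 it rises from 1.02 to 1.33 SD.

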Alexander et al compared four different smartphone application-based monitors: Instant Blood Pressure, Instant Blood Pressure Pro, Pulse Oximeter, and Pulse Oximeter Pro. Three different parameters were measured using these four devices: heart rate, blood pressure, and SpO₂. The comparison revealed a large degree of variance in the values between the Instant Blood Pressure, the Instant Blood Pressure Pro, the Pulse Oximeter, and the Pulse Oximeter Pro.⁹ Another study by Petersen and Dumont was conducted that compared the response of motion artifact of three different mobile pulse oximeter devices, all interfaced to Apple iPod Touch devices: the Nonin Xpod, the Masimo OEM inline module, and an Audio Phone Oximeter prototype. The study showed that there was more motion artifact at lower saturations for all three of the devices. The most valid measurements was found with Masimo's mobile device at readable values of approximately 85 to 87 percent.¹⁰

While the technology to detect SpO₂ and heartrates on smartphones is emerging and widely available, there is no evidence supporting its use in patients with lung disease. Smartphone pulse oximetry could be useful in individuals with acute or chronic lung disease; however, device inaccuracies could be harmful if desaturations are not detected immediately. It is not known how accurately these devices detect oxygen saturation/desaturation in patients with acute or chronic lung conditions. This study will be used to evaluate the accuracy of smartphone pulse oximeters in patients that will be undergoing a six-minute walk test in a pulmonary function lab.

Experimental Design and Methods

This is a prospective, observational study conducted at the pulmonary function laboratory at Rush University Medical Center. Subjects (n=48) will be selected if they are of 18 years of age or older, ambulatory, scheduled for a six-minute walk test, and agree to participate. The following information will be collected:

- First name
- Last name
- Date of Birth
- Age
- Height
- Gender
- Race/Ethnicity
- Oxygen use and frequency (if they are already on oxygen)
- Pulmonary Disorders
- Borg's Dyspnea Scale
- Heart rate (hospital-grade pulse oximeter and external and built-in smartphone pulse oximeter; pre- and post- test)
- SpO₂ (hospital-grade pulse oximeter and external and built-in smartphone pulse oximeter; pre- and post- test)

Procedures

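### The plan predicts parametric tests and leaves bias to a scatter plot, so nothing examines whether device error changes with saturation level

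*Combined protocol and SAP*

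**What the plan says.** Under Plans for Data Analysis, the device readings are to be summarised by mean and SD. The only test named is described thus: "A t-test will be used to determine any significant association between age, gender, diagnosis, weight, and oxygen use". After the alpha and beta values comes the sentence "It can be predicted that these tests will be parametric". No distribution check, transformation or alternative method follows. Agreement between devices is covered by one sentence: "A scatter plot will be used to assess bias and validity". No difference between devices, limits of agreement or summary by saturation level is defined. The outcomes are listed as "Dependent variables: SpO₂ and heart rate", with type of oximeter as the independent variable.

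The Aim of the Study includes episodes of desaturation. The Introduction says that "device inaccuracies could be harmful if desaturations are not detected immediately". It also describes a study of three mobile oximeters: "The study showed that there was more motion artifact at lower saturations for all three of the devices". The sentence after that reads: "The most valid measurements was found with Masimo's mobile device at readable values of approximately 85 to 87 percent".

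**The concern.** Accuracy for an individual patient depends on the spread of single-reading errors as well as on their mean. An overall SD is set mainly by the range in which most readings fall. If those are the higher saturations and errors are more variable at lower ones, an overall figure can look acceptable while being too narrow for desaturated patients, the group that the aim singles out.

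Predicting a parametric form in advance does not address this, and a scatter plot with no stated summary does not measure it. The Introduction's remark on motion artifact gives some reason to suspect error that depends on level, and half of the planned readings are taken after a walk. The plan has no step that would detect it.

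**Working it through.** **Inputs.** The protocol gives no error SD, no expected distribution of SpO₂ and no agreement margin, so there is no figure of its own to reproduce. It gives n = 48 (Experimental Design and Methods) and n = 30 (Inclusion criteria). That conflict is a separate matter, and both values are used here. Everything else below is assumed.

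**Step 1: effect of pooling two spreads.** Let *s* be the error SD at higher saturation (assumed 2 points), *r* the ratio of low-range to high-range SD, and *p* the share of low readings, with no mean bias.

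- Half-width of the overall limits: h = 1.96 × √[(1 − p)s² + p(rs)²]
- Correct half-width in the low range: 1.96 × rs
- Share of low readings inside the overall limits: 2Φ(h / rs) − 1

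Example with p = 0.20 and r = 2: h = 1.96 × √(0.8 × 4 + 0.2 × 16) = 1.96 × √6.4 = 4.96. The correct low-range half-width is 1.96 × 4 = 7.84. Coverage of low readings is 2Φ(4.96/4) − 1 = 78.5%. Coverage of high readings is 2Φ(4.96/2) − 1 = 98.7%.

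Coverage of low readings by nominal 95% limits:

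| Share low (p) | r = 1 | r = 1.5 | r = 2 | r = 3 |
|---|---|---|---|---|
| 10% | 95.0% | 83.4% | 73.6% | 61.9% |
| 20% | 95.0% | 85.6% | 78.5% | 70.8% |
| 30% | 95.0% | 87.5% | 82.3% | 77.2% |

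**Step 2: simulation with skew, rounding and a cap at 100.** One million readings were drawn with true SpO₂ = 100 − Gamma(shape 2.2, scale 2.6), which has a mean of about 94. About 11% of reference readings fall below 90. Reference noise SD is 0.8, and phone noise SD is 2 at 90 or above. The value 90 is for illustration only.

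| Phone SD below 90 | Reference readings below 90 outside the overall 95% limits |
|---|---|
| 2 (constant) | 3.8% |
| 3 | 14% |
| 4 | 26% |
| 6 | 35% |

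At 90 or above, 2 to 4% fall outside in every case. With SD 4 the overall limits are about −4.9 to +4.7, against about −7.7 to +8.1 for readings below 90. The first row shows that skew, rounding and the cap cause almost no understatement at low saturation. The effect comes from the assumed difference in spread.

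**Step 3: effect on t-tests.** For a t-test of a mean difference at n = 30 and n = 48, simulated type I error at a nominal 5% is 4.6 to 5.0% with mixed SDs and 5.2 to 5.4% with the ceiling (reference 98, SD 2). Means are well protected.

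**Step 4: how many low readings there would be.** At the assumed 11%, one time point gives 0.11 × 30 = 3.3 to 0.11 × 48 = 5.3 readings. Pooling pre- and post-walk readings gives 6.6 to 10.6, or about 7 to 11. Over shares of 10 to 30%, the pooled range is 0.10 × 60 = 6 to 0.30 × 96 ≈ 29. The 95% confidence interval for an SD is the estimate times √[(m − 1)/χ²], with the upper and lower 2.5% points of χ² on m − 1 degrees of freedom. With m = 5 it runs from 0.60 to 2.87 times the estimate. With m = 11 it runs from 0.70 to 1.75 times, before any allowance for two readings per patient.

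**The case against.** The strongest reply is that the plan contains no limits of agreement. Read in place, the sentence on parametric tests refers to the t-tests on age, gender, diagnosis, weight and oxygen use, so it sets no normal-theory limits that could be wrong. That stands. The more basic gap is that no agreement statistic is defined at all. Type I error of a t-test on a mean also changes little at these sample sizes, so the prediction does little harm to tests of means.

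A reader might infer that the protocol's background contradicts the parametric prediction by showing that error grows at low saturation. The documents do not support this. The passage concerns motion artifact, in devices not named as the Kenek Edge or Samsung S8 studied here. Its next sentence reports the most valid measurements at about 85 to 87 percent for one device. It gives a reason to check, and no more.

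A reader might also blame the cap at 100 for an apparent bias of about −0.4 points at high saturation. In the simulation, the bias at reference readings of 97 and above is −0.44 with the cap and −0.28 without it. Much of it is therefore regression to the mean from selecting on a noisy reference.

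Finally, limits of agreement for the low range alone may not be estimable with so few readings. That also stands, and the fix allows for it.

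**Conclusion.** The point holds as a gap in the analysis. The plan presumes a parametric form without a check, gives no numerical measure of agreement, and has no step to examine whether error varies with saturation, although its primary aim depends on performance during desaturation.

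An overall bias or set of limits could understate error at low SpO₂, but the documents cannot show that it would. The range of 62 to 88% coverage rests wholly on an assumed SD ratio of 1.5 to 3 and a low share of 10 to 30%. With a ratio of 1 there is essentially nothing to correct. That uncertainty is the reason to check rather than predict. The change is worth making because it is cheap and uses data already collected. It does not invalidate the planned covariate tests.

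**What to change.** In Plans for Data Analysis:

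1. Delete the sentence predicting parametric tests.
2. Replace the scatter-plot sentence with an agreement analysis of SpO₂ for each phone device against the Masimo. Plot the difference against the mean of the two readings, and report bias and 95% limits of agreement with confidence intervals.
3. Regress the difference on the mean (bias changing with level), and regress the absolute residual on the mean (spread changing with level). If spread changes, report regression-based limits in place of a single pair.
4. Pre-specify an SpO₂ level, chosen and justified by the investigators. List all paired differences below it and report the bias there. Pool pre- and post-walk readings with allowance for two readings per patient, and give limits for that range only if there are enough readings.

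The cost is a few lines of text and no extra data. The drawback is imprecision. If 11% of readings are low, the low-range results rest on about 7 to 11 pooled readings, and the report should say so. Confidence intervals for the overall limits will also be wide. With half-width t × √[1/n + 1.96²/(2(n − 1))] in SD units, they are about ±0.50 SD at n = 48 and ±0.65 SD at n = 30, taking one reading per patient.
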